## **10 ETHICAL CONSIDERATIONS**

### **10.1 Regulation statement**

Participation in the current study is on a volunteer basis and will only be possible when informed consent is obtained. Subjects can leave the study at any time for any reason if they wish to do so without any consequences. The investigator can decide to withdraw a subject from the study for urgent medical reasons. The study will be performed in accordance with

the declaration of Helsinki and the Dutch “Wet Medisch-wetenschappelijk Onderzoek met Mensen, WMO” (Medical Research Involving Human Subjects Act).

Patients can withdraw from this research at any time, without reason. Furthermore, patients can stop the study at any time, without consequences for the quality of treatment.

### **10.2 Recruitment and consent**

All patients that meet the inclusion criteria and do not have exclusion criteria will be asked to participate in the study. After full explanation of the study protocol informed consent will be obtained. Informed consent will be obtained from each participating patient in oral and written form prior to randomization. Informed consent will be obtained by a member of the research group.

### **10.3 Compensation for injury**

An insurance policy is signed with an insurance company for all patients in the study. They will be insured for injury or death due to participation in this study during the study period and for four years after termination of this study. A more detailed overview is given in appendix I.

## **11. ADMINISTRATIVE ASPECTS, MONITORING AND PUBLICATION**

### **11.1 Handling and storage of data and documents**

After obtaining written informed consent patients will be randomly assigned to one of two groups by randomization software (TENALEA Clinical Trial Data Management System). The randomization list was generated by this computerized program using random blocks with maximum block size 6, stratified by operation location (colon or rectum) and operation type (laparoscopic or open). Blinded, study-specific enteral feeding systems are prepared and coded according to this list. A corresponding randomization website will be used that generates the sequential randomization number corresponding to the stratified randomization list upon randomization of a patient.

The obtained results will be handled confidentially and will be accessible and viewed by study personnel, the Ethical commission, the Data Safety monitoring Board, the Health Inspection (Inspectie voor de Gezondheidszorg) and Danone/ Nutricia Research. Data will be coded so anonymity is preserved, also when data are published. The data and/or human material will be kept for 15 years in storage in the Catharina Ziekenhuis

### **11.3 Amendments**

Amendments are changes made to the research after a favourable opinion by the accredited METC has been given. All amendments will be notified to the METC that gave a favourable opinion.

All substantial amendments will be notified to the METC and to the competent authority.

Non-substantial amendments (for example typing errors or administrative changes) will not be notified to the accredited METC and the competent authority, but will be recorded and filed by the sponsor.

### **11.4 Annual progress report**

The sponsor/investigator will submit a summary of the progress of the trial to the accredited METC once a year. Information will be provided on the date of inclusion of the first subject, numbers of subjects included and numbers of subjects that have completed the trial, serious adverse events/ serious adverse reactions, other problems, and amendments.

### **11.5 End of study report**

The investigator will notify the accredited METC of the end of the study within a period of 8 weeks. The end of the study is defined as the last patient's last visit. In case the study is ended prematurely, the investigator will notify the accredited METC within 15 days, including the reasons for the premature termination. Within one year after the end of the study, the investigator/sponsor will submit a final study report with the results of the study, including any publications/abstracts of the study, to the accredited METC.

### **11.6 Publication of results**

Results will be analyzed and presented in scientific journals. The CCMO Statement Publication policy will be followed.

## 12. STRUCTURED RISK ANALYSIS

### 12.1 Potential issues of concern

The enriched enteral nutrition that is used, has been investigated before in healthy volunteers during endotoxemia. In this study there were no adverse or serious adverse events. Enclosed is the diet composition.

a. Level of knowledge about mechanism of action: The mechanism has been extensively shown in experimental models. A (pre) clinical study in healthy volunteers and a prospective randomized controlled trial in patients undergoing colorectal surgery showed results in line with the found hypothesis.

b. Previous exposure of human beings with the test product(s) and/or products with a similar biological mechanism. As mentioned before, the enteral nutrition that is used, has been investigated before in healthy volunteers during endotoxemia.

c. Can the primary or secondary mechanism be induced in animals and/or in *ex-vivo* human cell material? Yes

d. Selectivity of the mechanism to target tissue in animals and/or human beings. The found effects in previous studies is specifically targeting the inflammatory response and has shown to affect both anastomotic leakage and postoperative ileus, the two primary outcome parameters.

e. Analysis of potential effect. The nutrition itself is not considered to be harmful. Administration of enteral nutrition during surgery is a new concept. For this reason a data safety monitoring board is installed. There have been no described effects at all. A potential complication is aspiration pneumonia.

f. Pharmacokinetic considerations: *not applicable*

g. Study population. Patients undergoing colorectal surgery with primary anastomosis.

h. Interaction with other products: *not applicable*

i. Predictability of effect. The found effects in animal experiments were on both the inflammatory response and clinical parameters. The effects were consistent in various experimental models and in the clinical studies.

j. Can effects be managed? During surgery, gastric volumes are measured and gastric content is aspirated to minimize risk of aspiration pneumonia.

## **12.2 Synthesis**

The potential risk of this intervention is aspiration pneumonia. Several measures are taken to prevent this potentially increased risk.

1. Gastric content is aspirated; the volume of gastric content has been shown to be related to risk of aspiration pneumonia.
2. Nutrition is given postpylorically
3. A Data Safety Monitoring Board is installed.

## **APPENDIX II: DATA AND SAFETY MONITORING BOARD**

### **Roles and responsibilities**

The Data Safety and Monitoring Board (DSMB) is an independent group of experts that advises the participating investigators and the Institutional Review Board.

The members of the DSMB serve in an individual way and provide their expertise and recommendations. The primary responsibilities include:

1. Periodically review and evaluate the accumulated study data for participant's safety, the study conduct and progress
2. Make a recommendation to the investigators concerning continuation, modification or termination of the trial.

\* The DSMB considers study-specific data as well as relevant background knowledge about the disease or patient population under study.

\* The DSMB is responsible to define the processes, including the event triggers that would call for an unscheduled review, stopping guidelines and voting procedures prior to the first data review.

\* The DSMB is responsible for maintaining the confidentiality of its internal discussions and activities.

\* The DSMB should review each protocol for any major concern prior to implementation.

During the trial, the DSMB should review cumulative study data to evaluate the safety, the study conduct and the scientific validity and integrity of the trial.

It is the responsibility of the DSMB to provide a written report after each review with a recommendation to continue or terminate the study.

### **Documentation**

Each member of the DSMB will receive all documents as provided to the Medical Ethics Committee, including study protocol, ABR-form and patient information.

### **Membership**

The DSMB will consist of at least three members with relevant clinical expertise, clinical trial methodology and biostatistics. Members will be completely independent. Written documentation specifying the absence of any conflict of interest will be obtained. A chairperson will be appointed who will act as the spokesperson

### **Review and recommendation process**

It is the responsibility of the DSMB to:

- review the research protocol for data safety and monitoring
- evaluate the progress of the trial, including periodic assessments of data quality and timelines, participant recruitment, accrual and retention, participant risk versus benefit and other factors that can affect the study outcome.
- Consider factors external tot the study when relevant information becomes available, such as scientific or therapeutic developments that may have an impact on the safety of the participants or on the ethical conduct of the trial.
- Protect the safety of the study participants.
- Report on the safety and progress of the trial.
- Make a recommendation to the investigators concerning continuation, modification or termination of the trial.
- Ensure the confidentiality of the trial data and the results of the monitoring.

### **Meetings and reports**

The first meeting of the DSMB will be a face-to-face meeting before initiation of the trial to discuss the protocol and to establish the guidelines to monitor the study. During the course of the trial the DSMB will meet after inclusion of every 20 patients. These meetings may be convened as conference calls, as well as in person. An emergency meeting of the DSMB may be called at any time by the chairperson, the investigators or any other party involved in the trial. Meetings must be attended by all members and the DSMB may invite other parties involved in the trial, when necessary. The investigators will provide the DSMB with an overview / listing of the occurred events.

A formal report from the DSMB chair will be prepared and sent to all members of the DSMB within two weeks after the meeting. Once approved by all members of the DSMB, the report including a written statement (no safety concern/ safety concern) will be sent to the investigators and the Medical Ethics Committee.

### **Registration of events**

All Adverse Events (AE's) and Serious Adverse Events (SAE's) as mentioned in the protocol will be registered. Any SAE must be reported within 24 hours of knowledge by the investigator. All serious irreversible events will be reported to the DSMB on receipt. All reversible serious adverse events will be reported during the regular meetings.

[figure not shown]
In case the number of events is unacceptably high, the trial will be suspended and potentially prematurely terminated.

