### **8.2 Serious adverse events (SAEs)**

A serious adverse event is any untoward medical occurrence or effect that at any dose:

- results in death;
- is life threatening (at the time of the event);
- requires hospitalisation or prolongation of existing inpatients' hospitalisation;
- results in persistent or significant disability or incapacity;
- is a congenital anomaly or birth defect;
- Any other important medical event that may not result in death, be life threatening, or require hospitalization, may be considered a serious adverse experience when, based upon

appropriate medical judgement, the event may jeopardize the subject or may require an intervention to prevent one of the outcomes listed above.

Infectious complications and serious complications as a result of the operation that lead to prolongation of the patients' stay in the hospital will be registered as a SAE

The investigator will report the SAEs through the web portal ToetsingOnline to the accredited METC that approved the protocol, within 15 days after the sponsor has first knowledge of the serious adverse reactions.

SAEs that result in death or are life threatening should be reported expedited. The expedited reporting will occur not later than 7 days after the responsible investigator has first knowledge of the adverse reaction. This is for a preliminary report with another 8 days for completion of the report.

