### **8.5 Data and safety monitoring board**

An independent data and safety monitoring board (DSMB) will evaluate the progress of the trial and will examine safety variables. SAE's need to be reported to the principal investigator within 24 hours, some SAE's will be specified such as: re-intervention, respiratory failure, aspiration pneumonia, myocardial infarction, transfer to the ICU for any reason. Per 10 patients, individualized patient data will be presented to the DSMB. After full explanation of the data presented, the members of the DSMB discuss the consequences of the data presented separately. Besides the assessment of SAE's and AE's a safety analysis will be made after inclusion of 40 patients. In this analysis there is a special focus on gastric

volumes which will be compared as well as incidence of aspiration pneumonia. Adverse events will be listed and discussed with the DSMB. The outcome of the meeting of the DSMB will be discussed with the research group. The outcome will also be sent to the Medical Ethics Committee. All possible adverse events will be reported to the Central Committee on Research involving Human Subjects (Centrale Commissie Mensgebonden Onderzoek (CCMO)) and the IRB using the online module <https://toetsingonline.ccmo.nl>.

The DSMB includes:

1. Prof [name], Emeritus [name]
2. Dr. [name], Gastroenterologist
3. Dr. [name], Intensive Care Medicine
4. Dr. [name], Epidemiologist.

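### Appendix II gives reversible serious adverse events, which can include the trial's named risk of aspiration pneumonia, no automatic prompt route to the DSMB

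*Combined protocol and SAP*

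**What the plan says.** Appendix II, Registration of events, divides serious events by whether they can be reversed. For one group, "All serious irreversible events will be reported to the DSMB on receipt". For the other, "All reversible serious adverse events will be reported during the regular meetings". The available text neither defines reversible nor makes an exception for any event type.

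The plan gives two intervals for routine review:
- Appendix II, Meetings and reports: "During the course of the trial the DSMB will meet after inclusion of every 20 patients".
- Section 8.5: "Per 10 patients, individualized patient data will be presented to the DSMB".

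Other recipients have their own deadlines. Section 8.5 requires SAEs to reach the principal investigator within 24 hours and adds that "some SAE's will be specified such as: re-intervention, respiratory failure, aspiration pneumonia, myocardial infarction, transfer to the ICU for any reason". Section 8.2 allows 15 days for SAE reports to the ethics committee. For fatal or life-threatening SAEs it says "The expedited reporting will occur not later than 7 days after the responsible investigator has first knowledge of the adverse reaction".

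Appendix II also has unscheduled routes. Under Meetings and reports, "An emergency meeting of the DSMB may be called at any time by the chairperson, the investigators or any other party involved in the trial". Under Roles and responsibilities, the DSMB must define its processes before the first data review, "including the event triggers that would call for an unscheduled review".

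**The concern.** Sections 12.1(e) and 12.2 explain why the board exists: feeding during surgery is new, and aspiration pneumonia is the potential complication. Section 8.2 registers infectious complications that prolong hospital stay as SAEs. A pneumonia that prolongs the stay and then resolves is thus an SAE, and if it is judged reversible, Appendix II assigns it to the regular meetings. Section 8.5 singles out aspiration pneumonia and respiratory failure, but the 24-hour report goes to the principal investigator, not to the board.

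The sorting criterion is itself a problem. Reversibility is an outcome, and the person handling a report often cannot know it on the day. A life-threatening event from which the patient may recover has a 7-day deadline to the ethics committee but no stated deadline to the DSMB.

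At stake is how soon the body charged with watching a new risk learns of a case, and how many more patients are fed in the meantime.

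**Working it through.** **Inputs.** Accrual is at least 75-100 per year at the first centre, over an expected 3 years (Section 3). The sample size is 140 per group, or 280 in total (Section 4.5). The review interval is 20 patients (Appendix II, Meetings and reports) or 10 patients (Section 8.5). Ethics committee deadlines are 15 and 7 days (Section 8.2).

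**Check of the plan's own timeline.** 280 / 3 = 93.3 patients per year, inside 75-100. At the two limits, 280/100 = 2.8 years and 280/75 = 3.7 years. The stated 3 years is reproduced, so the accrual rate is a fair basis for turning patients into days.

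**Waiting time.** Longest wait in days = interval / annual accrual x 365.25. Mean wait = half of that, for an event at a random point in the interval. Lag = longest wait minus the ethics committee deadline, taking the event as known on the day it occurs and the review as held as soon as the count is reached.

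| Interval (patients) | Accrual per year | Longest wait (days) | Mean wait (days) | Longest wait minus 15 days | Longest wait minus 7 days |
|---|---|---|---|---|---|
| 20 | 75 | 97 | 49 | 82 | 90 |
| 20 | 100 | 73 | 37 | 58 | 66 |
| 10 | 75 | 49 | 24 | 34 | 42 |
| 10 | 100 | 37 | 18 | 22 | 30 |

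The last column applies only to fatal or life-threatening events. Irreversible events, deaths included, go to the board on receipt, so in practice it concerns life-threatening events judged reversible.

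**Added centres.** Section 3 continues the trial in several centres without giving their accrual. As an assumption, doubling accrual to 150-200 per year shortens the longest wait at 20 patients to 37-49 days (20/200 and 20/150 x 365.25). Tripling it to 225-300 per year gives 24-32 days.

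**Patients exposed.** The interval counts inclusions, so this figure does not depend on accrual. With equal groups, about half of those included in an interval are fed: 20/2 = 10, or 10/2 = 5. These are approximate upper limits for an event just after a review.

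**Number of reports.** The documents give no risk of aspiration pneumonia. At an assumed 1-5%, 280 x 0.01 = 2.8 and 280 x 0.05 = 14 cases over the trial. This is an upper bound on delayed pneumonia reports, because only cases judged reversible would wait.

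**The case against.** The strongest objection is that the plan provides ways round the regular meeting. Any party may call an emergency meeting, and the principal investigator, who knows of the event within 24 hours, could do so. The DSMB must set its own triggers for unscheduled review, and it meets before the trial starts to establish its monitoring guidelines. This stands in part. A reader might infer that every reversible event is held back until the next regular meeting, or that the DSMB is always the last to know; the documents do not support either. But the emergency meeting is discretionary, the triggers are not set in the visible text, and both depend on someone first passing the event on. The harm meeting in Section 8.6 likewise begins only once the DSMB suspects harm.

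A second objection concerns size. A reader might infer that the board routinely hears months after the ethics committee. A lag of about two months or more needs the 20-patient interval, close to the longest wait, and roughly single-centre accrual. At 10 patients, the mean wait of 18-24 days is only 3-9 days beyond the 15-day deadline. Nor is 7 days the general comparator. This objection stands.

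Third, no passage says that aspiration pneumonia usually resolves, and a case of unknown outcome might equally be sent on receipt. That is fair. The point needs only that some cases may be classed as reversible, and the uncertainty shows that the criterion does not settle the routing.

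Fourth, prompt review of the gravest events with periodic review of the rest is a legitimate design, and Section 8.5 adds a 40-patient analysis that covers aspiration pneumonia. True, but that analysis is a single look, and the split used does not identify the gravest events: a life-threatening event can be reversible.

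Finally, a figure directly after the rule is not shown and may bear on event handling. Its absence is not held against the plan.

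**Conclusion.** The point holds as a gap in the reporting rule. The visible text gives reversible SAEs no automatic prompt route to the DSMB. They can include an aspiration pneumonia or a life-threatening event that may recover, and the criterion that decides is often unknown when it has to be applied.

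At first-centre accrual the longest wait is about 73-97 days on the 20-patient schedule or 37-49 days on the 10-patient data flow. The mean is about half, and calendar times fall as centres join. Independently of accrual, up to about 10 (or 5) further patients may be fed before the board routinely sees the case.

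These figures assume equal allocation, review as soon as the count is reached, and no use of the unscheduled routes. The documents do not support saying that such events never reach the board early, nor that a lag of months behind the ethics committee is typical. This is an inexpensive improvement to safety oversight and leaves the efficacy analysis untouched.

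**What to change.** In Appendix II, Registration of events, replace the reversible/irreversible split with routing by event type, for example:

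*Deaths, life-threatening events, aspiration pneumonia and respiratory failure are copied to the DSMB chair together with the 24-hour report to the principal investigator, whatever the expected outcome. Other SAEs are reported at the regular meetings.*

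Reconcile the 10-patient data flow in Section 8.5 with the 20-patient meetings in Appendix II, stating whether the former is a meeting or only a transfer of data. Then align Sections 8.2 and 8.5 with the new routing.

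The cost is a few lines of text and one copied notice per listed event. For aspiration pneumonia that is about 3-14 notices over the trial at the assumed 1-5% risk; the documents give no rates for the other listed events. The downside is a small number of extra notices to the chair. Only reporting changes, not patient management.

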**CASE REPORT FORM**Patiënt identificatie nummer: Randomisatienummer: **Patiëntgegevens**

Geb datum: \_\_\_ / \_\_\_ / 19\_\_

Geslacht: M / V

Lengte: \_\_\_\_\_ cm                      Gewicht \_\_\_\_\_ kg

ASA klasse:            1 / 2 / 3 / 4 / 5

SNAQ score:

MUST score:

Roken:                       Nee                       JaAlcohol:                     Nee                       Ja

dagelijks / wekelijks / maandelijks

Abdominale chirurgie in de voorgeschiedenis:

 Nee                       Ja: \_\_\_\_\_

Bestaand colostoma

 Nee                       Ja: \_\_\_\_\_**Huidige situatie**Diabetes                     Nee Jainsuline  Nee                       Ja

Gebruik van psychofarmaca:

 Nee                       Ja: \_\_\_\_\_

Dosering: \_\_\_\_\_

Gebruik van statine:  Nee Ja: \_\_\_\_\_

Dosering: \_\_\_\_\_

Gebruik van PPI:     Nee Ja: \_\_\_\_\_

Dosering: \_\_\_\_\_

Gebruik van aspirine:

 Nee                       Ja: \_\_\_\_\_

Dosering: \_\_\_\_\_

Maligniteit:             Nee Ja

Afstand tumor tot de anus: \_\_\_\_\_ cm

Neoadjuvante beh:  Nee Ja

chemo / RT / CRT \_\_\_\_\_

Preop bloedtransfusie:     Nee                       Ja \_\_\_\_\_Preop NSAID:             Nee Ja

Welke \_\_\_\_\_ start \_\_\_ / \_\_\_ / 20\_\_

Dosering: \_\_\_\_\_ stop \_\_\_ / \_\_\_ / 20\_\_

Dag van opname: \_\_\_ / \_\_\_ / 20\_\_; Tijdstip \_\_\_:\_\_\_ uur

